#### 10.3.7 Patient Reported Outcome of EQ-5D

Analyses of changes and/ or percent changes from baseline will be analyzed for each scheduled postbaseline visit and for the final visit for the EQ5D instrument and the EQ VAS. Patients who do not have both a baseline measurement and at least one postbaseline measurement will not be included.

The final visit is defined as the last assessment within 28 days after date of last dose of oral study drug or within 5 months of last IV study drug, whichever is later. For the protocol-specified post-baseline visits; the EQ-5D-5L assessment will be grouped in actual scheduled visit windows as described in Table 3. If more than one assessment date falls within a given visit window, the one that is closest to the actual scheduled EDC visit date will be used. In the case of ties, the assessment prior to the scheduled visit date will be used. The data sets should highlight the value for the patient that was included in the summary table, wherever feasible. The summary tables and graphs will only display data if the number of observations is greater than 10 in each treatment arm.

At a given visit, the change from baseline will be analyzed for the treatment comparisons using an Analysis of Covariance (ANCOVA) with treatment and stratification variables as categorical factors and baseline measurement for the parameter as a continuous covariate. In addition, a graphical presentation of mean changes over time may be presented.

#### 10.3.8 Assess Mutations in non-tBRCA HRR Genes as a Molecular Marker of Efficacy

Patients will be required to provide archival tumor tissue or a screening biopsy for central laboratory analysis prior to enrollment. Genes of interest will be sequenced using Foundation Medicine's NGS test, which examines a panel of cancer-related genes, including BRCA1/2. The invPFS for the subset of patients with non-tBRCA HRR genes will be explored and compared for the treatment comparisons.

#### 10.3.9 Evaluation of Post-Progression Efficacy Endpoints

Following treatment discontinuation, subsequent anti-cancer treatments will be collected for all patients every 12 or 24 weeks ( $\pm$  14 days), until death, loss to follow-up, withdrawal of consent from study, or closure of the study. The subsequent anti-cancer data with start and stop date and any date of progression is documented. The date of progression may be a

Confidential 37 of 52

documented event per RECIST guidelines or may be an event of symptomatic/clinical or CA-125 progression. The following endpoints will be derived based on this data.

- Chemo-Free Interval (CFI), will be calculated in months as the time since the last dose of the most recent chemotherapy regimen to the date of the first dose of a subsequent chemotherapy + 1 day. Patients without a documented start of a subsequent chemotherapy after study drug will be censored on the date of their last available assessment.
- Time to First Subsequent anti-cancer Treatment (TFST), will be calculated in months as the time from randomization to the date of the first dose of the first subsequent anti-cancer treatment regimen + 1 day. Patients without a documented start date of a subsequent anti-cancer treatment after study drug will be censored on the date of their last available assessment.
- Time to Second Subsequent anti-cancer Treatment (TSST), will be calculated in months as the time from randomization to the date of the first dose of the second subsequent anti-cancer treatment regimen + 1 day. Patients without a documented start of a second subsequent anti-cancer treatment after study drug will be censored on the date of their last available assessment.

The same statistical test used for the primary endpoint (ie, stratified log rank test and a stratified Cox proportional model) will be used to compare treatments for this endpoint.

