#### 10.3.7 Evaluation of Post-progression Efficacy Endpoints

Following treatment discontinuation, subsequent anticancer treatments will be collected for all patients every 12 or 24 weeks ( $\pm$  14 days), until death, loss to follow-up, withdrawal of consent from study, or closure of the study. The subsequent anticancer data with start and stop date and any date of progression documented for each regimen will be recorded. The following endpoints will be derived based on these data.

- Chemotherapy-free interval (CFI), will be calculated in months as the time since the last dose of the most recent chemotherapy regimen to the date of the first dose of a subsequent chemotherapy, or death due to any cause, + 1 day. Patients without a documented start of a subsequent chemotherapy after study drug will be censored on the date the patient was last known to be alive or last visit.
- Time to first subsequent anticancer treatment (TFST), will be calculated in months as the time from randomization to the date of the first dose of the first subsequent anticancer treatment regimen, or death due to any cause, + 1 day. Patients without a documented start date of a subsequent anticancer treatment will be censored on the date the patient was last known to be alive or last visit.
- Time to second subsequent anticancer treatment (TSST), will be calculated in months as the time from randomization to the date of the first dose of the second subsequent anticancer treatment regimen, or death due to any cause + 1 day. Patients without a documented start of a second subsequent anticancer treatment will be censored on the date the patient was last known to be alive or last visit.
- Time to treatment discontinuation of oral dose (TDT), will be calculated in months as the time from randomization to the date of the last dose of oral treatment + 1 day. Patients still ongoing will be censored at the last visit prior to the visit cutoff.

The same statistical test used for the primary endpoint (ie, stratified log rank test and a stratified Cox proportional model) will be used to compare treatments for this endpoint.

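### The ATHENA-COMBO SAP leaves death out of CFI, TFST and TSST, although the ATHENA-MONO SAP and COMBO's own PFS2 count it (minor; exploratory endpoints)

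*SAP*

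**What the plan says.** **ATHENA-COMBO SAP, 10.3.9.** Each of the three endpoints ends only when a later therapy begins:

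- CFI runs to "the date of the first dose of a subsequent chemotherapy + 1 day".
- TFST runs to the "date of the first dose of the first subsequent anti-cancer treatment regimen + 1 day".
- TSST runs to the "date of the first dose of the second subsequent anti-cancer treatment regimen + 1 day".

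For TFST, patients with no recorded "start date of a subsequent anti-cancer treatment after study drug will be censored on the date of their last available assessment". CFI and TSST carry the same rule. The SAP does not define which assessment is meant. The arms are compared with the stratified log-rank test and stratified Cox model used for the primary endpoint. No competing-risk analysis is planned.

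**ATHENA-MONO SAP, 10.3.7.** The same endpoints include death. TFST runs to the "date of the first dose of the first subsequent anticancer treatment regimen, or death due to any cause, + 1 day", TSST to "the first dose of the second subsequent anticancer treatment regimen, or death due to any cause + 1 day", and CFI is worded likewise. Patients without an event are censored when last known alive or at the last visit.

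**Elsewhere in the COMBO SAP.** PFS2 (10.3.3) uses the same follow-up on subsequent treatment. It counts death as an event and censors at last known alive or last visit. Section 10.3 states that the exploratory analyses carry no multiplicity adjustment.

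The protocol does not define CFI, TFST or TSST. Neither SAP explains why the definitions differ, and COMBO's Table 2 of protocol amendments does not mention it.

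**The concern.** Two SAPs for one trial give the same endpoint names to different quantities, and one of them departs from its own handling of death in PFS2. Under COMBO 10.3.9 a patient who dies before starting next therapy leaves the risk set as an ordinary censored observation. Kaplan-Meier, log-rank and Cox then treat her as if she could still have started therapy later.

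What is at stake is how the post-progression results read. The COMBO medians would be longer than medians computed by MONO's rule. Arm B, which is in both comparisons, would also be analysed under two definitions. A reader comparing the reports could not separate the effect of definition from that of longer follow-up.

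**Working it through.** The documents state no figure for these endpoints, so there is none to reproduce. The check traces individual patients through the two rules, then sizes the effect under stated assumptions.

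**1. Who is treated differently.**

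- An Arm B patient who starts next therapy before both data cut-offs has the same TFST under either SAP.
- An Arm B patient who dies without next therapy has an event at death under MONO. Under COMBO she is censored at an assessment on or before death.
- For TSST, the same split applies to deaths after the first but before the second subsequent therapy.
- Living patients without next therapy are censored under both SAPs, possibly on different dates.

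**2. Effect on the median.** Assumed inputs, none from the documents: constant independent hazards; median time to next therapy or death of 24 months; share *p* of first events that are untreated deaths of 5%, 10% or 20%.

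- Composite hazard: λ = ln 2 / 24 = 0.0289 per month.
- Hazard of starting therapy: λ(1 − p).
- Median with death censored: ln 2 / [λ(1 − p)] = 24 / (1 − p).

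| p | 24 / (1 − p) | Increase | Simulated, censored at death | Simulated, censored at last 12-weekly assessment |
|---|---|---|---|---|
| 5% | 24 / 0.95 = 25.3 | 5% | 25.2 | 25.1 |
| 10% | 24 / 0.90 = 26.7 | 11% | 26.6 | 26.5 |
| 20% | 24 / 0.80 = 30.0 | 25% | 30.1 | 29.8 |

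Medians are in months. The simulation used 400,000 patients per row with administrative censoring uniform over 36 to 60 months. Its composite medians were 23.9, 24.0 and 24.1. Leaving out death drives the difference; the choice of censoring date adds little.

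**3. Effect on the hazard ratio.** Under the same model, death-censored HR = composite HR × (1 − p_A) / (1 − p_B). Starting from a composite HR of 1.00:

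- 5% in both arms: 0.95 / 0.95 = 1.00.
- 10% in A, 5% in B: 0.90 / 0.95 = 0.95.
- 5% in A, 10% in B: 0.95 / 0.90 = 1.06.
- 15% in A, 5% in B: 0.85 / 0.95 = 0.89.

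The ratio moves only when untreated deaths differ by arm, and it can move either way.

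**4. What the death-censored curve describes.** It is not the share of patients who actually start therapy either. With p = 20% at 24 months, 1 − KM = 1 − 0.5^0.8 = 42.6%, while the true share who have started is 0.8 × 0.5 = 40%. Time to treatment alone therefore needs a cumulative-incidence estimate.

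**The case against.** The case against is substantial, and much of it stands.

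- **Low stakes.** The endpoints are exploratory. They are absent from the protocol's exploratory objectives (2.3) and from COMBO's list of exploratory efficacy variables (9.4). This stands and sets the severity.
- **A different estimand, not an error.** Time to treatment with death censored targets the cause-specific hazard, which is legitimate. Suppose therapy starts at 0.0289 per month in both arms, with untreated deaths at an assumed 0.3% per month in A and 0.1% in B. The composite HR is (0.0289 + 0.003) / (0.0289 + 0.001) = 1.07 and the cause-specific HR is 1.00. Each correctly answers its own question. This stands for the hazard ratio. But the SAP does not say that it wants the cause-specific quantity, and it plans no cumulative incidence to accompany it.
- **Censoring date.** For living patients, stopping at the last assessment of treatment status is defensible, and nothing says telephone contacts are excluded. Only the missing definition remains as a fault.

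A reader might infer three stronger things that the documents do not support:

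- **That the rule hides harm from the combination.** No document figure suggests that untreated deaths differ between Arms A and B. An excess would still show in invPFS, OS and PFS2, all of which count death.
- **That the two read-outs cannot be compared.** Each is its own randomised comparison. MONO's primary analysis used a 23 March 2022 cut-off, so Arm B figures would differ at the later COMBO read-out even under one definition.
- **That patients who die untreated are scored as having avoided therapy for good.** They are censored, not counted as permanently treatment-free.

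**Conclusion.** The point holds as a minor one. COMBO 10.3.9 omits death from three endpoints for which MONO 10.3.7 includes it, departs from COMBO's own PFS2, gives no reason, and leaves its censoring date undefined.

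Measured against MONO's definition, Kaplan-Meier times to next therapy are overstated by about 5% to 25% if untreated deaths make up 5% to 20% of first events. That range, the 24-month median and the constant independent hazards are assumptions. If untreated deaths are equally common in both arms, the medians lengthen but the hazard ratio does not change. The invPFS and OS analyses, the alpha allocation and the power are untouched.

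**What to change.** In COMBO SAP 10.3.9, add death from any cause as an event for CFI, TFST and TSST. Replace the censoring rule with MONO's: the date last known alive or the last visit. This restores one definition for Arm B across the two SAPs and matches PFS2 within COMBO.

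If the sponsor wants time to treatment alone, say so and give the reason. Define which assessment sets the censoring date, and report cumulative incidence with death as a competing event.

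The first option costs SAP wording and the matching programming. Death and last-alive dates are already needed for OS (COMBO 10.2.2), so no new data are required. The second option adds a cumulative-incidence analysis for each endpoint.

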10.3.10 Other Exploratory Endpoints described in a separate report

The following exploratory endpoints that are mentioned in the protocol will be summarized in a separate statistical report:

- To study variants in circulating tumor DNA (ctDNA) as markers of response and resistance
- To characterize PK of rucaparib as monotherapy and in combination with nivolumab
- To characterize PK of nivolumab as a monotherapy and in combination with rucaparib
- To evaluate immunogenicity of nivolumab when administered as a monotherapy and in combination with rucaparib
- To explore exposure-response relationship between selected exposure measures of rucaparib and nivolumab, and safety and efficacy endpoints

#### 10.4 Examination of Efficacy in Subgroups

The primary endpoint (invPFS) may be further explored within the ITT population for subgroups.

- The stratification factor used for randomization.
  - HRD classification (tBRCA, non-tBRCA LOHhigh, non-tBRCA LOHlow, and non-tBRCA LOHunknown)

Confidential 38 of 52

- o Disease status (no residual disease vs residual disease)
- o Timing of surgery (primary surgery vs. interval debulking).
- PDL1 expression as described in section 10.3.1
- Age groups ( $< 65, 65-74, \ge 75$ )
- Race (White, Other, Unknown)
- Prior use of Bevacizumab (Yes or No)
- Mutation: BRCA1 vs BRCA2
- Mutation type: Germline, Somatic, or unknown
- Country (for registration requirements), eg, Japan, South Korea

Confidential 39 of 52

#### 11 SAFETY ANALYSIS

Safety and tolerability is one of the secondary study objectives. Overall safety and tolerability will be measured by the incidence of adverse events, serious adverse events, adverse events leading to discontinuation, deaths, specific laboratory abnormalities (worst grade) and changes from baseline.

The safety analyses will be presented for the safety population presenting the data for each treatment group separately (Arm A [rucaparib and nivolumab], Arm B [rucaparib], Arm C [nivolumab], and Arm D [placebo]). The analyses will be presented by the actual treatment given. Patients randomized to either treatment group containing IV Nivolumab (ie, Arm A or Arm C) who never receive Nivolumab, will be analyzed in the analogous treatment group containing IV Placebo (ie, Arm B or Arm D, respectively).

Summary tables are based on data that are found to be "on-treatment"/ "treatment-emergent" for the oral or IV study drug as outlined in the below sections.

All safety data which is considered treatment-emergent will be summarized. Treatment-emergent is defined as safety data with an onset date on or after the date of first dose of study medication until the date of last dose of oral study drug plus 28 days or date of last IV dose plus 5 months (ie, 152 days), whichever is the latest date.

Descriptive statistics of safety will be presented using the NCI CTCAE v5.0. All AEs, drug-related adverse events, serious adverse events (SAEs) and drug-related SAEs will be tabulated using the worst grade per NCI CTCAE v5.0 by system organ class and preferred term. On-study lab parameters including hematology, coagulation, chemistry, liver function, thyroid, adrenal and renal function will be summarized using worse grade by NCI CTCAE v5.0.

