- u = First dose of IV study drug occurs C2D1. Study treatment continues on Day 1 every 28-day cycle until 24 months after initiation of oral/IV combination study treatment, disease progression, or unacceptable toxicity, whichever happens first.

Table 5. Schedule of Assessments for All Patients (cont.)

- V = AEs, SAEs, and AESIs that occur after first administration of study drug through to 28 days after last dose of oral or IV study drug, whichever occurs later, and AEs/SAEs assessed as related to IV drug that occur up to 5 months after the last IV dose of study drug will be recorded. In addition, AEs that were related to a screening procedure will also be recorded. Section 8 includes the details of reporting AEs, SAEs, and AESIs. Ongoing SAEs, AESIs, or treatment-related Grade 3/4 AEs will be followed to resolution or stabilization. After the 28-day (oral) or 5-month (IV) windows, only SAEs considered as potentially study-drug related (including serious reports of pneumonitis or similar events, ie, interstitial lung disease, pulmonary fibrosis, acute interstitial pneumonitis, alveolitis necrotizing, alveolitis, hypersensitivity pneumonitis, and organizing pneumonia, if considered to be related to study drug), and AESIs of myelodysplastic syndrome (MDS) and acute myeloid leukemia (AML) regardless of causality, will be recorded. If a patient discontinues from treatment and begins a subsequent anticancer therapy, the sponsor will terminate collection of SAEs, with the exception of the AESIs of MDS and AML.
- w = An optional tumor biopsy may be collected from patients at time of disease progression/randomized treatment discontinuation. Additional consent is required. Refer to the central Laboratory Manual for detailed sample collection and handling instructions.
- x = All patients discontinued from treatment, regardless of reason, should be followed for subsequent treatments, secondary malignancy, and survival every 12 weeks (± 14 days) after SFU1 (28-days after the last dose of study drug) until death, loss to follow-up, withdrawal of consent from study, or closure of the study. Follow-up can be performed via the telephone. Diagnosis of any secondary malignancy requires appropriate documentation (ie, laboratory and/or pathology reports) and should be reported as specified in Section 8.7.

Table 6. Pharmacokinetic and Immunogenicity Sample Collections

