7.4.6 Long-term Follow-up (LTFU)

Patients who complete the Safety Follow-up Visit(s) after the last dose of study treatment will continue in long-term follow-up as described below.

- Disease assessment for patients who discontinued treatment for reason other than disease progression or death. Tumor scans should continue to be performed at 12-week intervals (up to 7 days prior permitted) relative to C2D1 for the first 3 years and every 24 weeks thereafter until radiologic disease progression by RECIST v1.1, as assessed by the investigator, is documented;
- CA-125 measurement should be performed at the same time as radiological imaging;
- Subsequent treatments, secondary malignancy monitoring, and OS information will be collected for all patients every 12 weeks (± 14 days) until death, loss to follow-up, withdrawal of consent from study, or closure of the study, starting 12 weeks after SFU1. Follow-up can be performed via the telephone. Diagnosis of any secondary malignancy requires appropriate documentation (ie, laboratory and/or pathology reports) and should be reported as indicated in Section 8.7;
- SAEs assessed as potentially related to study drug, and AESIs of MDS and AML irrespective of causality, are to be reported as specified in Section 8.7;
- SAEs unrelated to IV drug do not need to be captured after the 28-day follow-up visit/period. Only those related or possibly related to IV drug should be captured until the 5-month SFU2.

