7.5.4.2 Clinical Laboratory Investigations

With the exception of urinalysis samples, all other samples collected will be analyzed by a central laboratory; a duplicate sample may be collected and analyzed by the local laboratory for immediate eligibility/ treatment decisions. If a patient has a known, clinically significant laboratory abnormality and/or associated symptoms that would require AE management or interruption of the IV study drug, either central or local laboratory tests should be analyzed prior to each administration of an IV drug infusion. The panels of laboratory tests to be performed are shown below:

Hematology: RBC and parameters (hemoglobin, hematocrit, MCV, MCH, and MCHC) and reticulocyte count, WBC and differential (with ANC), and platelet count will be assessed for all patients at screening, during treatment at each study visit, and at the Treatment Discontinuation Visit, 28-day SFU1, and at the 5-month SFU2, if toxicities are present. Hematology results must be reviewed by the investigator before the start of study drug and ongoing at times testing occurs. Additional and more frequent tests may be performed at the investigator's discretion.

Clinical Chemistry: total protein, albumin, creatinine or estimated GFR using the Cockcroft-Gault formula or institutional standard formula, BUN or urea, total bilirubin, ALP, ALT, AST, LDH, glucose, sodium, potassium, magnesium, chloride, bicarbonate (CO₂,/HCO₃-), calcium, phosphorus, TSH, Free triiodothyronine (T3; fT3); Free thyroxine (T4, fT4) at screening; TSH with reflexive fT3 and fT4 if TSH is abnormal on treatment, folic acid (first 6 cycles only), and total cholesterol will be assessed for all patients at screening, during treatment at each study visit, and at the Treatment Discontinuation Visit, 28-day SFU1, and at the 5-month SFU2, if toxicities are present. Fasting is not required before blood sampling. If pancreatitis is suspected clinically, serum lipase and amylase should be analyzed. Serum chemistry results must be reviewed by the investigator before the start of treatment with study drug and ongoing at times testing occurs.

In addition to the clinical chemistry assessments above, serology serum for hepatitis C antibody and hepatitis B surface antigen should be performed at screening. Testing for HIV must also be performed at screening if mandated locally by a given site.

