8.6 Pregnancy or Drug Exposure During Pregnancy

Pregnancy is an exclusion criterion. In addition, due to inclusion criteria #4, requiring at least a bilateral salpingo-oophorectomy and partial omentectomy, women of child-bearing potential will not be randomized in this study.

All study participants must avoid pregnancy achieved through assisted reproductive technology, for the duration of study treatment and for a minimum of 6 months following the last dose of study drug (oral or IV, whichever is later).

8.7 Recording of Adverse Events, Serious Adverse Events, and Adverse Events of Special Interest

Events that occur after signing of informed consent but prior to initiation of study drug, unless due to a protocol-mandated procedure, should be recorded on the Medical History eCRF; however, events are to be reported as SAEs if serious and related to a protocol-mandated procedure during this time. Any AE (serious or non-serious) that occurs after first dose of study drug through 28 days after receiving the last dose of oral or IV study drug, whichever occurs later, will be recorded on the AE eCRF. Additionally, only AEs that are related to IV drug that occur between 28 days and 5 months after the last dose of IV drug will be recorded on the AE eCRF.

After the 28-day reporting window following discontinuation of randomized treatment, only SAEs assessed as potentially related to study drug should be reported.

After the 28-day or 5-month reporting window after discontinuation of randomized treatment, AESIs of MDS and AML, irrespective of causality, should be reported.

• AESIs of pneumonitis or similar events should only be reported up to, but not beyond, the SFU1 (28-days after the last dose of rucaparib). After this period, only events considered serious and related to study drug should be reported as SAEs (including serious reports of pneumonitis or similar events, ie, interstitial lung disease, pulmonary fibrosis, acute interstitial pneumonitis, alveolitis necrotizing, alveolitis, hypersensitivity pneumonitis, and organizing pneumonia), if considered to be related to study drug.

Information on the follow-up of AEs, SAEs, and AESIs is provided in Section 8.8.

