#### 11.1 Adverse Events

AEs will be classified using the MedDRA version 22.0 or higher classification system. The severity of the toxicities will be graded according to the National Cancer Institute Common Terminology Criteria for Adverse Events (NCI CTCAE) v5.0 or later. Treatment-emergent adverse events (TEAEs) are defined as events with an onset date on or after the date of first dose of study medication until the date of the last oral study medication plus 28 days or date of last IV dose plus 5 months (ie, 152 days), whichever is the latest date. Also, AEs will be considered treatment-emergent if all or part of the date of onset of the adverse event is missing and it cannot be determined if the AE meets the definition for treatment-emergent.

The number and percentage of patients who experienced TEAEs for each SOC and PT will be presented. Multiple instances of the TEAE in each SOC and multiple occurrences of the same PT are counted only once per patient. The number and percentage of patients with at least one TEAE will also be summarized.

Separate tables will be presented as follows:

- All TEAEs;
- TEAEs by CTCAE grade;
- Grade 3 or greater TEAEs;
- Treatment-related TEAEs, for oral treatment and IV treatment separately, and also both;
- Serious TEAEs;
- TEAEs with an outcome of death;
- TEAEs leading to discontinuation of study medication for oral treatment and IV treatment separately, and also both;
- TEAEs resulting in reduction oral study medication;
- TEAEs resulting in interruption of oral treatment and IV treatment separately, and also both;
- TEAEs resulting in reduction or interruption of oral treatment;
- Time to the first TEAE that results in a reduction of oral treatment;
- Time to the first TEAE that results in an interruption of oral treatment or IV treatment separately, and also both;
- Time to the first TEAE that results in discontinuation of oral treatment or IV treatment separately, and also both.

The incidence of TEAEs will be summarized by relationship to either oral or IV study drug according to the following categories: "treatment-related," or "not treatment-related". If a patient experiences multiple occurrences of the same AE with different relationship categories, the patient will be counted once, as a relationship category of treatment related.

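### COMBO safety tables present all-cause AEs and worst laboratory grades to 152 days after the last IV dose, but late collection is restricted: non-serious AEs only if IV-related, SFU2 laboratory tests only if toxicities are present

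*SAP*

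**What the plan says.** **Analysis window.** COMBO SAP section 11 ends the treatment-emergent period at the last oral dose plus 28 days or "date of last IV dose plus 5 months (ie, 152 days), whichever is the latest date". Section 11.1 repeats these limits for TEAEs and section 11.3 for laboratory values. Membership depends on onset date alone. Over this window section 11.1 lists tables of all TEAEs, Grade 3 or greater TEAEs, serious TEAEs and "TEAEs with an outcome of death", and splits TEAEs into treatment-related and not treatment-related. Section 11.3 summarizes maximum, minimum and last laboratory values and shifts to the worst on-treatment grade. Protocol 9.7.1 and 9.7.2 use the same 5-month window, so the SAP follows the protocol.

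**AE collection.** Under Protocol 8.7, any AE from first dose "through 28 days after receiving the last dose of oral or IV study drug, whichever occurs later, will be recorded on the AE eCRF". After that, the form takes "only AEs that are related to IV drug that occur between 28 days and 5 months after the last dose of IV drug". Table 5 footnote v agrees: "AEs/SAEs assessed as related to IV drug that occur up to 5 months after the last IV dose of study drug will be recorded". Protocol 7.4.6 adds that "SAEs unrelated to IV drug do not need to be captured after the 28-day follow-up visit/period".

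**Laboratory collection.** Protocol 7.5.4.2 schedules hematology and chemistry at each treatment visit, at treatment discontinuation, at SFU1, and "at the 5-month SFU2, if toxicities are present". Table 5 footnote c and Protocol 7.4.5.3 give the same condition.

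**The concern.** A table of all TEAEs is normally read as all-cause incidence. Here the first part of the window is all-cause and the last part, for non-serious events, contains only what an investigator attributed to the IV drug. The result is neither all-cause incidence nor drug-related incidence. The not-treatment-related category suffers most: for late non-serious events the recording rule leaves it almost empty by design, apart from events that a table might class as unrelated to oral drug only.

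The laboratory tables have a related weakness. A worst-grade summary that takes in an SFU2 sample drawn only when toxicities are present adds values from a selected group of patients.

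Arm B is also reported under two conventions. The ATHENA-MONO SAP (section 11.1) stops at the last oral dose plus 28 days, while COMBO can run to the last IV dose plus 152 days. Safety is a secondary objective, so what is at stake is how the safety incidences can be read, not the primary test.

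**Working it through.** **The plan's own figure.** 5 × 365.25/12 = 152.19, which rounds to the stated 152 days.

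**Length of the restricted span.** Let day 0 be the last IV dose and L the number of days that oral drug continues after it.

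- Treatment-emergent end (COMBO SAP 11) = max(L + 28, 152)
- All-cause recording end (Protocol 8.7) = max(L, 0) + 28
- Restricted span = the first minus the second

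| L (days) | Treatment-emergent end | All-cause end | Restricted span | Share of days to the treatment-emergent end |
|---|---|---|---|---|
| 0 or less* | 152 | 28 | 124 | 81.6% |
| 28 | 152 | 56 | 96 | 63.2% |
| 56 | 152 | 84 | 68 | 44.7% |
| 84 | 152 | 112 | 40 | 26.3% |
| 112 | 152 | 140 | 12 | 7.9% |
| 124 | 152 | 152 | 0 | 0% |

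*Oral drug stopped on or before the day of the last IV dose.

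For L above 124 the span stays at 0. The documents give no distribution for L, so these values are an assumed range. If all-cause tables stop where all-cause recording stops, the span is 0 for every L.

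**Which events are restricted.** The passages divide as follows.

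- *Non-serious AEs.* Protocol 8.7 and Table 5 footnote v agree on IV-related only. Protocol 7.5.2 fits this: after the 28-day visit it records concomitant medication only if given for IV-related AEs. Non-serious AEs related to oral drug alone also drop out.
- *SAEs, AESIs and fatal events.* The protocol contradicts itself. Table 5 footnote v, 7.4.6 and part of 8.7 limit late capture by relatedness (MDS and AML excepted), and 8.2 limits fatal events more than 28 days after the last dose to treatment-related ones. Another part of 8.7, and 8.10, require SAEs and AESIs regardless of relationship to 5 months after IV drug. Section 8.10 then itself restricts SAEs to potentially related ones after the 28-day window.
- *Subsequent anticancer therapy.* SAE collection ends when it starts, except for MDS and AML (Protocol 3.1.6, 7.5.4.1 and Table 5 footnote v). The SAP window has no matching cut.

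**Which measurements are restricted.** At SFU2 only hematology and chemistry are conditional. Protocol 7.4.5.3 lists vital signs without condition.

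**The case against.** The strongest opposing text is Protocol 7.5.4.1, which says that patients are monitored for all AEs, SAEs and AESIs to 28 days after oral drug and 5 months after IV drug. Read literally, it removes the mismatch. But that section refers to Section 8 for complete details, and the recording rule in 8.7 is specific about what goes on the form. The objection does stand in part: late all-cause capture of SAEs and AESIs is disputed, not absent. Even if 8.7 and 8.10 are read as requiring it, the all-TEAE table still combines all-cause serious events with related-only non-serious events.

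The size is limited. The 124 days are a maximum. For a patient who completes treatment, 28 days of Cycle 1 plus about 730 days of combination plus 152 days gives about 910 days, and 124/910 is about 14%. Each patient counts once per preferred term, so many late events would change nothing. The influence of one conditional laboratory visit after long routine testing is also limited. SFU1 tests are unconditional and, with a window of ±7 days, can fall after day 28; patients still on oral drug have tests at every cycle visit. Late values therefore do not come only from patients with toxicity.

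Section 11.1 already tabulates treatment-related TEAEs for oral drug, IV drug and both, and section 11.2 covers immune-mediated AEs. These help with drug-related incidence, but they do not repair the all-cause tables.

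**Conclusion.** The mismatch is real and is shared by the COMBO SAP and Protocol 9.7.1 and 9.7.2. It is firm for non-serious AEs and for SFU2 hematology and chemistry, and unresolved for SAEs, AESIs and fatal events. The restricted span runs from 124 days to 0, depending on how long oral drug outlasts IV drug. Its effect on incidence cannot be computed from the documents.

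A reader might infer more, and the documents do not support it:

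- *That 82% of the safety window is compromised.* 124/152 is a share of post-dose days when oral drug does not outlast IV drug. It is not a share of events or of the whole window.
- *That the comparison of Arm A with Arm B is biased by a different rule.* Every arm receives IV drug or IV placebo, and the window and recording rule are the same in all four.
- *That vital signs are selectively collected.* They are scheduled at SFU2 for all patients.
- *That unrelated late deaths and SAEs are missing.* The protocol text conflicts and does not settle this.

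This is an inexpensive improvement in interpretability. It does not threaten the trial's main conclusions.

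**What to change.** 1. **Reconcile the protocol text** on late SAE, AESI and fatal-event capture: Table 5 footnote v, 7.4.6, 8.2 and the relatedness-limited part of 8.7 against 7.5.4.1, the all-cause part of 8.7, and 8.10. State in the SAP which rule was applied on the eCRF.
2. **Add all-cause TEAE and worst-grade laboratory tables** that stop 28 days after the later of the last oral or IV dose. State how SFU1 samples taken up to day 35 (28 + 7) are handled, since they are unconditional. Leave the vital-sign summaries as they are.
3. **Show all later recorded events to day 152 separately:** IV-related and immune-mediated AEs, all SAEs, AESIs including MDS and AML, and deaths, with a footnote on the capture rule. Limiting this table to IV-related and immune-mediated AEs would lose late unrelated SAEs, oral-related SAEs and MDS/AML from both displays.
4. **Keep the protocol-defined 152-day tables** as a supplement with the same footnote, so the protocol definition is still reported.

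The cost is wording and one extra table set. The headline TEAE count would be slightly lower, and late nivolumab toxicity would move from the headline table to the separate late table.
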